## 1.2 Schema

#### 1.4 Schedule of Events

Activity	Screening	Preparatory Session (Baseline)	Ketamine Sessions 			Integration Session	Follow-Up 		
			1	2	3		14 Days	30 Days	90 Days
Visit						0	(±3)	(±7)	(±7)
(Window in days)	-60	0							
Informed Consent	X								
Demographics	X								
Medical History	X								
Eligibility Criteria	X								
Registration 	X								
Clinical and Laboratory Assessments									
Vital Signs 	X		X 	X 	X 				
Physical Exam	X								
ECOG Score	X								
ECG	X		ACI						
Adverse event collection 	X	X	X	X	X	X	X		
Concomitant medications	X	X	X	X	X	X	X		
Complete Metabolic Panel	X								
Urine Drug Screen	X								
Pregnancy Test 	X								
Study Intervention									
Evaluation and Screening 			X	X	X				

Activity	Screening	Preparatory Session (Baseline)	Ketamine Sessions 			Integration Session	Follow-Up 		
			1	2	3		14 Days	30 Days	90 Days
Visit						0	(±3)	(±7)	(±7)
(Window in days)	-60	0							
Ketamine Administration 			X	X	X				
Psychotherapy		X	X	X	X	X			
Assessments									
EDS 	X	X	X	X	X		X	X	X
QIDS-SR-16 		X	X	X	X		X	X	X
C-SSRS Baseline/Screening 	X								
C-SSRS Since Last Visit 		X	X	X	X	X	X		
MEQ-30 			X	X	X				
NADA 			X	X	X				
DADDS 		X	X	X	X		X	X	X
FACIT-Sp 		X					X	X	X
Storyline Integrative Assessment 		X					X	X	X

---

 Ketamine will be given during three sessions, 2 to 7 days apart. Questionnaires, with the exception of the MEQ, may be completed up to 1 day prior to the ketamine session.

 Follow-up will be based on time since completion of the integration session.

 To register eligible patients on study, complete a Clinical Trials Office Subject Registration Form and submit to [[contact]](mailto:[contact]).

 Laboratory assessments should be completed within 28 days of enrollment.

 Vital signs include systolic/diastolic blood pressure, heart rate, respiration rate, pulse oximetry and weight.

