#### 2.3.3 To assess the effect that KAP has on symptoms of existential distress and depression in patients with non-operable GI cancers as measured by the Spiritual Well-Being (FACIT-Sp)

Exploratory Endpoint: Mean change in score on FACIT-Sp from baseline to Day 30 post completion of intervention.

**2.3.4** To develop an algorithm with Storyline Health technology to rapidly discover the most predictive and information rich components in the assessment of existential distress and its treatment response.

Exploratory Endpoint: Identification of a behavioral phenotype that better predicts a response to ketamine intervention.

**2.3.5** To evaluate the completion rate of questionnaires using the Storyline platform.

Exploratory Endpoint: The percentage of questionnaires completed.

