### **3.3 Storyline Health Assessments**

#### **3.3.1 Overview**

Storyline is a flexible research platform that will be used to deliver assessments during the course of the study. Storyline extracts features from video, audio, and natural language and overlays it with other data sources like patient records, genome data and outcomes.

Participants are owners of their data and can access it at any time, and even delete it. However, the study will not be able to provide direct meaningful interpretations for participants. Note, that participants may be able to choose some non-research interactions within the Storyline app, such as what celebrities they look like. This is not considered a benefit nor will be included in the research data, it's for entertainment purposes for the participants.

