#### **3.3.2 Storyline Core Questions of Health**

The baseline assessment is designed to mimic a typical clinical psychiatric diagnostic interview and a neurological assessment. The psychiatric portion is a 60- minute program broken into six different 10-minute assessment sessions. The neurological portion is a 10-mintute assessment.

Patients will be notified through the Storyline app on their smartphone or smart device to complete the various study assessments. Storyline manages reminders and makes the process simple.

The objective is to create an effective and fast algorithm for feature selection and question selection to build assessments, diagnostic biobehavioral markers and predictive models from Storyline captured speech, vocal and facial data. The proposed algorithm has 3 components, including (1) rapid feature and question filtering based on variance, (2) feature selection using a method that integrates mutual information and random forest importance scores and (3) question selection using a deep learning method that ranks the predictive value of each question using the optimized features. The steps are as follows:

**Rapid Question Filtering** – The first step in the Short Story algorithm will be to filter questions, assessments and A.I. features in the storyARC and storyTIME files that have little information content. To do this, we will compute the variance for each measured feature for each question in the data for all people in a customer's pilot study. The variance is scaled to account for differences in units. We then sum the variance for each feature for each question, apply a min-max absolute scale for interpretation that scores questions from 0 (low information content) to 100 (high information content). The results will enable users to rapidly screen, rank and prune questions with little to no information content by pruning the bottom 25% of tested candidate questions.

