### **3.3.4 Deep Cognitive and Behavioral Assessments During Treatment**

Participants will be asked to perform a 10-minute “Well-being” assessment that includes open-ended questions about major domains of health. Examples include how they are, concerns, physical symptoms, emotional symptoms, social interactions and perceived support, medications and missed pills, energy and activity, sleep, a 1-5-minute story describing something that happened to them during the week and tests of short-term memory, working memory and attention.

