## 7.3 Patient Reported Outcomes

The response to study therapy will be assessed utilizing the Existential Distress Scale (EDS), Quick Inventory of Depressive Symptomatology (QIDS-SR-16), Patient Health, Columbia-Suicide Severity Rating Scale Baseline/Screening and Since Last Visit (C-SSRS), Death

Transcendence Scale (DTS), Functional Assessment of Chronic Illness Therapy - Spiritual Well-Being (FACIT-Sp), , Nondual Awareness Dimensional Assessment (NADA), Mystical Experiences Questionnaire (MEQ-30), Storyline Integrative Assessment, Patient-Reported Experience on Study Therapy, at the time points indicated in the Schedule of Events.

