### 9.5 Exploratory Objectives

Exploratory endpoints include 1) the mean change in score on EDS and QIDS-SR-16 from baseline to 2 weeks post completion of intervention; 2) the correlation between total score on the MEQ-30 and NADA and change in the EDS score at the 2 week primary outcome time point;

and 3) the mean change in score on FACIT-Sp from baseline to Day 30 post completion of intervention.

An additional exploratory objective is to develop an algorithm with Storyline Health technology to rapidly discover the most predictive and information rich components in the assessment of burnout and its treatment response. The associated endpoints are 7) the identification of a behavioral phenotype that better predicts a response to ketamine intervention; and 8) the Storyline questionnaire completion rate.

Analysis of the above exploratory endpoints will be descriptive. Continuous variables will be summarized by the minimum, maximum, mean, standard deviation, and 95% confidence interval. The Storyline completion rate and 95% exact binomial confidence interval will be reported. Spearman rank correlation coefficients will be used to summarize the correlation between the total score on the MEQ-30 and NADA and change in the EDS score at the 2-week primary outcome time point.

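### The exact binomial interval on the Storyline completion rate treats repeated forms from 12 subjects as independent, so it is too narrow when completion clusters within subject

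*Combined protocol and SAP*

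**What the plan says.** Section 2.3.5 sets an objective about completion of questionnaires on the Storyline platform, with the endpoint "The percentage of questionnaires completed". Section 9.5 lists it as "the Storyline questionnaire completion rate" and gives the analysis in one sentence: "The Storyline completion rate and 95% exact binomial confidence interval will be reported". Section 5.5.1 fixes enrolment at 12 subjects.

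The plan does not say which forms make up the denominator, and its sections point in different directions:

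- The Schedule of Events (Section 1.4) has one row for the "Storyline Integrative Assessment", marked at baseline and at the 14-, 30- and 90-day follow-ups. Section 7.3 also names it as a separate item: "Mystical Experiences Questionnaire (MEQ-30), Storyline Integrative Assessment, Patient-Reported Experience on Study Therapy".
- Section 3.3.2 describes the baseline psychiatric portion as "broken into six different 10-minute assessment sessions", plus a neurological part. Section 3.3.4 describes a shorter "assessment that includes open-ended questions about major domains of health".
- Section 3.3.1 is broader: "Storyline is a flexible research platform that will be used to deliver assessments during the course of the study".

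Section 9 contains no method for repeated forms within a subject: no cluster adjustment, design effect, subject-level bootstrap or per-subject definition of completion.

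**The concern.** A Clopper-Pearson interval assumes independent yes/no trials with a common probability. Forms from one person are unlikely to meet that assumption: some subjects will complete nearly everything and others will skip repeatedly. Pooling them lets the form count stand in for sample size, although the study has only 12 independent units.

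Elsewhere the plan uses the exact interval on one yes/no per person, for study completion (Section 9.3) and for meeting the Existential Distress Scale (EDS) criteria (Section 9.4.2). Section 9.5 moves the same interval to a different unit without adjusting it.

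What is at stake is an overstated precision for platform completion, in a pilot that Section 3.1 says will inform a larger randomised trial. The point estimate is unaffected.

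**Working it through.** The plan states no numerical figure for this interval, so there is none to reproduce.

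**Inputs from the documents.** There are 12 subjects. The forms per subject, m, depend on the reading:

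- m = 4: the Storyline row of the Schedule of Events (baseline, 14, 30 and 90 days), giving 12 × 4 = 48 forms.
- m = 10: six psychiatric parts + one neurological part at baseline + one assessment at each of three follow-ups, giving 120 forms.
- m = 35: all post-screening self-report forms: EDS 7 + QIDS-SR-16 7 + DADDS 7 + FACIT-Sp 4 + Storyline 4 + MEQ-30 3 + NADA 3 = 35, giving 420 forms. The interviewer-rated C-SSRS and the screening EDS are left out.

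**Assumed inputs.** The documents give no ICC or completion rate. I used ICC 0 to 0.5 and completion of 80%, 90% and 95%.

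**Effective sample size.** The design effect is 1 + (m − 1) × ICC, and the effective n is 12m divided by it. At ICC 0.3:

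- m = 4: 1 + 3 × 0.3 = 1.9; 48/1.9 = 25.3
- m = 10: 1 + 9 × 0.3 = 3.7; 120/3.7 = 32.4
- m = 35: 1 + 34 × 0.3 = 11.2; 420/11.2 = 37.5

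Going from 48 to 420 forms adds about 12 effective observations, but the planned interval would count 372 more.

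**Exact coverage of the nominal 95% pooled interval.** Each subject's completed count is beta-binomial with mean p and the given ICC. The total is the 12-fold convolution. Coverage is the probability of all totals whose Clopper-Pearson limits contain p.

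| Forms per subject | Completion | ICC 0 | ICC 0.1 | ICC 0.3 | ICC 0.5 |
|---|---|---|---|---|---|
| 4 | 80% | 95% | 92% | 85% | 78% |
| 4 | 90% | 98% | 95% | 90% | 84% |
| 4 | 95% | 99% | 98% | 95% | 93% |
| 10 | 80% | 96% | 86% | 71% | 61% |
| 10 | 90% | 97% | 88% | 73% | 61% |
| 10 | 95% | 97% | 88% | 71% | 57% |
| 35 | 80% | 96% | 66% | 45% | 36% |
| 35 | 90% | 96% | 67% | 45% | 36% |
| 35 | 95% | 96% | 66% | 42% | 30% |

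Without clustering the interval behaves as intended. With it, coverage falls below 95% except with 4 forms at 95% completion (roughly nominal) or 4 forms at 90% completion and ICC 0.1.

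**What would be printed.**

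- 36 of 48 forms: 60.4% to 86.4%, 26 points wide. Clopper-Pearson at the effective n of 25.3 (ICC 0.3) gives 53.9% to 89.9%, 36 points.
- 336 of 420 forms: 75.8% to 83.7%, about 8 points wide, from 12 people.

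**Drop-out.** Assume 3% to 10% of subjects leave before each later visit and 90% to 100% of forms are done while on study.

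- If forms due after study withdrawal or death count as missed, coverage is 35% to 48% with 35 forms. With 4 forms it is 81% to 90% when the hazard applies before all six later visits, or 85% to 96% when it applies only between the four Storyline visits.
- If only forms due while on study count, coverage is about 96% or more, so drop-out adds no clustering.
- Stopping treatment alone is not drop-out here, because Section 6.7 keeps those subjects in follow-up.

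**Candidate replacements** (simulation, 40,000 runs, ICC 0.1 to 0.5):

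- Korn-Graubard, with the design effect estimated from the 12 subjects: coverage 95% to 96% at 80% completion for every form count; at 95% completion, above 99% with 4 or 10 forms but 84% to 94% with 35.
- A t interval on subject proportions: 90% to 94% at 80% completion, but 68% to 88% at 95%.
- Exact binomial on a subject-level yes/no (at least 80% of forms done): 96.5% to 99.6%.
- Mean width at 80% completion and ICC 0.3, pooled against Korn-Graubard: 23.5 against 35.8 points (4 forms), 14.7 against 31.9 (10), 7.7 against 29.8 (35).

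**The case against.** The strongest reply is that Section 9.5 never says the forms will be pooled. A percentage at each scheduled visit, or one yes/no per subject, would make the exact interval valid: with n = 12 its coverage is 98% or more at 80%, 90% and 95% completion. The plan's other completion rate, in Sections 9.1 and 9.3, is a subject-level quantity. This does not remove the point. Section 2.3.5 makes the questionnaire the unit, and Section 9.5 describes one rate with one interval. If a subject-level rate was meant, the text must say so.

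A second reply is that the lowest coverages need 35 forms. That is fair. The Schedule of Events and Section 7.3 list the Storyline assessment separately from the other scales, and several appendix scales are laid out as paper forms to be circled and signed. Section 3.3.1 allows the broad reading but does not establish it. The ten-form count likewise treats each ten-minute part as its own questionnaire. The four-form figures are the best supported, and there the loss is modest unless the ICC is about 0.3 or more.

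It also stands that no document supports any particular ICC, that the drop-out figures depend on the assumed hazard and denominator, and that the analysis is labelled descriptive. These points limit the size of the problem; they do not make the interval correct.

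**Conclusion.** The concern holds and is minor. As written, the interval has its stated coverage only if completion is independent across forms from the same person, and nothing in the plan makes that likely or corrects for its failure.

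On the best-supported count of four forms, the shortfall at 80% completion runs from 3 points at ICC 0.1 to 17 points at ICC 0.5, and there is essentially none at 95% completion. On the wider counts the interval is seriously too narrow at every ICC from 0.1 upward. The ICC, completion rate and form count are all assumed. The undefined denominator is part of the same defect, since the answer depends so strongly on it. No decision, test or primary result depends on this interval.

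**What to change.** Replace the Storyline sentence in Section 9.5 with text that does three things:

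1. Defines the denominator: which forms are expected per subject, and whether forms due after study withdrawal or death count as missed or are excluded.
2. Reports the pooled percentage of expected forms descriptively, with the median and range of per-subject completion and no pooled exact binomial interval.
3. Gives an interval that respects the 12 subjects. One option is an exact binomial interval on a pre-stated subject-level yes/no, such as completing at least a stated share of expected forms. The other is a cluster-aware interval on the pooled percentage, such as Korn-Graubard with the design effect estimated from the data.

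The cost is one or two sentences and no new data. Each option has a price. The subject-level interval is wide (9/12 gives 42.8% to 94.5%; 11/12 gives 61.5% to 99.8%), needs a chosen cut-off and describes subjects rather than forms. Korn-Graubard keeps the form as the unit and needs no assumed ICC, but still under-covers with 35 forms and very high completion. It also needs a stated fallback if every form is complete, because the design effect cannot then be estimated. A plain t interval on subject proportions is reasonable near 80% completion but not at high completion.

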 Cardiovascular measures during KAP session (blood pressure, O2 sat, heart rate) will be completed within ten minutes prior to session and at 40 min and 2 hours post-administration. Vitals will be reviewed by an on-site MD with ACLS certification. A crash cart and code response team will be available.

 Adverse events and conmeds will be recorded at the time of the session. Subjects may also be contacted by study staff after the session to assess for any additional adverse events or conmed changes.

 Pregnancy test (serum or urine) must be obtained at screening and  $\leq$  8 days prior to ketamine administration for all women of childbearing potential and as clinically indicated while on trial.

 Evaluation and screening to include the items listed in Section 6.1.2.

 Ketamine will be administered according to Section 6.1.3.

 Existential Distress Scale (EDS). See Appendix 2.

 Quick Inventory of Depressive Symptomatology (QIDS-SR-16). See Appendix 3.

 Columbia-Suicide Severity Rating Scale Baseline/Screening (C-SSRS). See Appendix 4.

 Columbia-Suicide Severity Rating Scale since Last Visit (C-SSRS). To be completed at any time during study participation if a subject is rated as of moderate or high risk on the Baseline/Screening C-SSRS. See Appendix 5.

 Mystical Experiences Questionnaire (MEQ-30) should be completed after ketamine administration. See Appendix 8.

 Nondual Awareness Dimensional Assessment. See Appendix 7.

 Death and Dying Distress Scale. See Appendix 9.

 The Functional Assessment of Chronic Illness Therapy. See Appendix 6.

 See Section 3.3.

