#### 2.3.2 To assess the effect that qualitative experiential aspects of the ketamine experience have on subsequent change to depression and existential distress measures using the Mystical Experiences Questionnaire (MEQ-30) and Nondual Awareness Dimensional Assessment (NADA)

Exploratory Endpoint: Correlation between total score on the MEQ-30 and NADA and change in the EDS score at the 2 week primary outcome time point.

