### 5.1 Inclusion Criteria

1.  Subject aged  $\geq$  18 years.
2.  Subjects with non-operable GI cancers requiring multi-modal treatment (e.g. surgery +/- chemo +/-radiation) and have a high likelihood of recurrence and/or treatment failure in the opinion of the treating investigator.
3.  Screen positivity for existential distress on the EDS, defined as scoring  $\geq$  3 on any of the 10 component domains, or a total score  $\geq$  6
4.  ECOG Performance Status  $\leq$  2.
5.  Adequate hepatic function as defined as:
  - Total Bilirubin  $\leq$  1.5x institutional upper limit of normal (ULN) unless elevated bilirubin is related to Gilbert's Syndrome
  - AST(SGOT)/ALT(SGPT)  $\leq$  3  $\times$  institutional ULN
    - Subjects with liver metastases will be allowed to enroll with AST and ALT levels  $\leq$  5  $\times$  ULN.
6.  For subjects of childbearing potential: Negative pregnancy test or evidence of post-menopausal status. The post-menopausal status will be defined as having been amenorrheic for 12 months without an alternative medical cause. The following age-specific requirements apply:
  - Subjects  $<$  50 years of age:
    - Amenorrheic for  $\geq$  12 months following cessation of exogenous hormonal treatments; and
    - Luteinizing hormone and follicle-stimulating hormone levels in the post-menopausal range for the institution; or
    - Underwent surgical sterilization (bilateral oophorectomy or hysterectomy).
  - Subjects  $\geq$  50 years of age:
    - Amenorrheic for 12 months or more following cessation of all exogenous hormonal treatments; or
    - Had radiation-induced menopause with last menses  $>1$  year ago; or

- Had chemotherapy-induced menopause with last menses >1 year ago; or
- Underwent surgical sterilization (bilateral oophorectomy, bilateral salpingectomy, or hysterectomy).

7.  Subjects of childbearing potential and subjects with a sexual partner of childbearing potential must agree to use a highly effective method of contraception as described in Section 5.3.1.

8.  Subjects with a sexual partner of childbearing potential must agree to use a condom during intercourse for 24 hours post- ketamine dose.

9.  Agree to refrain from using any psychoactive drugs, including alcoholic beverages, ondansetron, cannabis, and non-routine PRN medications within 24 hours of each ketamine administration. Exceptions include daily use of caffeine, nicotine, and opioid pain medication (see Section 6.5.1).

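### The MEQ-30/NADA correlation in section 9.5 uses raw EDS change, ignores the baseline EDS already collected, and does not say which session score enters

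*Combined protocol and SAP*

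**What the plan says.** The endpoint in section 2.3.2 is "Correlation between total score on the MEQ-30 and NADA and change in the EDS score at the 2 week primary outcome time point". Section 9.5 repeats it and names the method: "Spearman rank correlation coefficients will be used to summarize the correlation between the total score on the MEQ-30 and NADA". The second variable is the raw EDS change at 2 weeks. The section names no covariate, session or rule for combining sessions. It also says "Analysis of the above exploratory endpoints will be descriptive". Intervals are promised there for continuous summaries and for the Storyline completion rate, but not for the correlation coefficient.

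Other sections bear on this:

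- **Sessions.** The Schedule of Events (section 1.4) says "Ketamine will be given during three sessions, 2 to 7 days apart" and marks MEQ-30 and NADA at all three. Under section 2.1, attending two of the three counts as completion, so completers may have two or three scores per instrument.
- **Timing.** Footnote 15 says "Mystical Experiences Questionnaire (MEQ-30) should be completed after ketamine administration". Footnote 1 says "Questionnaires, with the exception of the MEQ, may be completed up to 1 day prior to the ketamine session". NADA is not excepted, although Appendix 7 asks the patient to rate what has just been experienced.
- **Baseline.** EDS is recorded at screening and again at the preparatory session, which the Schedule labels as baseline.
- **Entry.** Criterion 3 in section 5.1 requires a score of at least 3 "on any of the 10 component domains, or a total score" of at least 6. Appendix 2 has ten items scored 0 to 4.

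**The concern.** There are two gaps.

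First, a patient with a low EDS total has little room to fall, so raw change tends to follow the baseline score. That part of the variation in change has nothing to do with the ketamine experience. If baseline is unrelated to the experience score, it acts as noise and pulls a real correlation towards zero. If baseline is related to the experience score, it also creates a correlation where none exists.

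Second, the endpoint speaks of one score per instrument while the schedule produces up to three. The first, last, highest or mean score could each be meant, and the choice could be made after the data are seen.

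Section 3.1 says the study will inform a larger randomized trial. A coefficient carried into that design should have a fixed definition and an interval.

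**Working it through.** The plan states no expected correlation, power or alpha for this analysis, so there is no figure to reproduce.

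**1. EDS range at entry.** One item at 3 and nine at 0 gives a total of 3. Ten items at 4 gives 10 × 4 = 40. Totals of 3 to 40 therefore qualify. This range applies at screening, which may take place up to 60 days before the preparatory session. The baseline total is measured at that session and need not lie in the range.

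**2. Set-up.** From the documents: n = 12 (section 9.1), Spearman's method, EDS change at 2 weeks. Assumed: baseline EDS uniform on 3 to 30; a mean fall of 40% of baseline (SD 25%); a correlation *c* between baseline and the experience score of 0 to 0.4; and, for a real association, a correlation of 0.5 between the experience score and the proportional fall. There were 40,000 simulated trials per setting, with a fall in EDS counted as positive. The adjusted coefficient, computed on ranks with M = experience score, D = fall and B = baseline, is

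r(MD·B) = [r(MD) − r(MB)·r(DB)] / √[(1 − r(MB)²)(1 − r(DB)²)].

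**3. Results.** Baseline and fall correlate at about 0.55.

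| Setting | Mean raw rho | Mean partial rho |
|---|---|---|
| Real association, c = 0 | 0.33 to 0.34 | 0.41 |
| No association, c = 0 | 0.00 | 0.00 |
| No association, c = 0.2 | 0.11 | 0.01 |
| No association, c = 0.4 | 0.21 to 0.22 | 0.01 |

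Hand check:

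- With no association given baseline, r(MD) is about r(MB)·r(DB): 0.2 × 0.55 = 0.11 and 0.4 × 0.55 = 0.22.
- With c = 0 and a real association, the partial is about raw/√(1 − 0.55²): 0.34/0.835 = 0.41.

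**4. Sensitivity.** Under other assumptions (baseline and follow-up EDS correlated 0.3 to 0.7, or a 3–40 scale with different proportional changes), baseline correlates with change at 0.33 to 0.59 in size. At c = 0.3, the spurious raw rho is 0.09 to 0.16 in size. The mean partial rho stays within about 0.03 of zero throughout.

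**5. Precision.** By Fisher's z with SE = √[(1 + rho²/2)/(n − 3)], an observed rho of 0.5 gives SE = √(1.125/9) = 0.354 and a 95% CI of −0.14 to 0.85. Adjusting for one covariate replaces 9 by 8, giving SE = 0.375 and a CI of −0.18 to 0.86. The sampling SD of rho with no association is about 0.30 raw and 0.32 partial.

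**6. Open session choice.** With no association and an assumed between-session correlation of 0.3 to 0.7, the three session coefficients differ by a median of 0.28 to 0.41. The median largest |rho| of the three is 0.34 to 0.38, against 0.21 for one fixed score.

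**The case against.** The strongest reply is that this is a descriptive coefficient in a 12-patient feasibility study, where success is defined by completion (section 9.1). The shifts in step 3 are smaller than the sampling SD of about 0.3. Section 2.3.2 asks about change, and raw change answers that literally; a partial coefficient answers a slightly different question. All of this stands. It limits the severity, and it is why the adjusted coefficient should sit beside the planned one and not replace it.

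A reader might draw stronger conclusions that the documents do not support:

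- **That the wide entry range by itself biases the result.** It does not. With the experience score unrelated to baseline, mean raw rho is 0.00 even though baseline and change correlate at 0.55. Bias also needs baseline EDS to be related to MEQ-30 or NADA, and no figure for that is given.
- **That the open session choice inflates a false-positive rate.** Taking the largest of three would raise the chance of passing a 5% critical value from 5% to 11–14%. The plan attaches no test, threshold or alpha to this coefficient, so that is not an error rate of the plan.

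The two gaps remain. Exploratory status does not define the score to be used, and baseline EDS is collected in any case.

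**Conclusion.** The point holds and is minor. As written, the coefficient cannot be computed without a further choice of session score, and it leaves out a covariate that is already collected. Under the assumed proportional falls, omitting baseline reduces a real association from about 0.41 to about 0.33. It produces a spurious mean of 0.00 to 0.22 only as the correlation between baseline and experience score goes from 0 to 0.4. The dilution rests on the assumed link between baseline and change; the spurious part also rests on the second correlation, which may be zero. No primary, secondary or safety conclusion depends on this analysis.

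For NADA there is a separate inconsistency. Footnote 1 of the Schedule permits completion before the session, while Appendix 7 asks about an experience just had. Until these are reconciled, NADA scores could mix the time before and after administration.

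**What to change.** In section 9.5:

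- Define one value per patient per instrument: the mean over the ketamine sessions attended. This also covers completers with two sessions. Peak or last score could be argued for; what matters is that one rule is fixed before the data are seen.
- Report the partial Spearman correlation of that value with Day-14 EDS change, adjusted for the preparatory-session EDS total, with a 95% CI, beside the planned raw coefficient.
- Label session-specific coefficients as supporting only.

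In the Schedule of Events, reconcile footnote 1 with Appendix 7, so that only NADA scores completed after administration enter this analysis.

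The cost is a few sentences and a few lines of code. No new visits or data items are needed. Adjustment uses one degree of freedom and widens the interval slightly: at an observed 0.5, from −0.14 to 0.85 to −0.18 to 0.86.
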